6.9. Baseline and Other Summaries and Analyses

6.9.1. Baseline Summaries

Demographics, medical history, primary diagnosis, history of prior AD treatments and disease characteristics including variables defined in [Section 3.4](#) will be summarized by treatment group according to CaPS. Baseline disease severity based on IGA and baseline EASI score will also be summarized by gender and by age group (adults and adolescents).

6.9.2. Study Conduct and Subject Disposition

Subjects evaluation, disposition, discontinuation will be summarized according to CaPS.

6.9.3. Study Treatment Exposure

A summary of dosing compliance by treatment group will be provided.

² For purposes of analysis, Other will comprise the categories of American Indian or Alaska Native, Native Hawaiian or Other Pacific Islander, Multi-Racial and any other category reported on the CRF.

The exposure to study drug will be summarized by the total number of days of dosing, mean / median number of days of exposure and number and percent of subjects in exposure duration categories.

6.9.4. Concomitant Medications and Non-drug Treatments

Prior drug and non-drug treatment, concomitant drug and non-drug treatment will be summarized according to CaPS.

6.10. Safety Summaries and Analyses

Safety analysis will be based on the SAF analysis set.

All clinical AEs, SAEs, TEAEs, withdrawal due to AEs, ECGs, vital signs and safety laboratory data will be reviewed and summarized on an ongoing basis during the study to evaluate the safety of subjects.

Safety data will be presented in tabular and/or graphical format and summarized descriptively, where appropriate. All safety endpoints will be listed and summarized in accordance with CaPS. Categorical outcomes (eg, AEs) will be summarized by subject counts and percentage. Continuous outcomes (eg, blood pressure, pulse rate, etc.) will be summarized using N, mean, median, standard deviation, etc. Change from baseline in laboratory data, ECGs and vital signs will also be summarized. Subject listings will be produced for these safety endpoints accordingly.

6.10.1. Adverse Events

The safety data will be summarized in accordance with CaPS. All safety data will be summarized descriptively through appropriate data tabulations, descriptive statistics, categorical summaries, and graphical presentations. Safety endpoints for the study include:

- Treatment-emergent AEs and SAEs;
- Withdrawals from active treatment due to AEs;
- Serious infections, defined as any infection (viral, bacterial, and fungal) requiring hospitalization or parenteral antimicrobials.

Treatment-emergent AEs will also be analyzed using a 3-tier approach. Risk differences between the active treatments and placebo will be used to summarize the results.

For Tier-1 events, point estimates, 95% confidence intervals and p-values will be presented graphically comparing each active dose group with placebo. No multiplicity adjustments will be made. For Tier-2 events, only point estimates and 95% confidence intervals will be presented graphically (see [Section 5.2.6](#)). Tier-3 events will be summarized as part of the overall AE summaries, AEs will be displayed by MedDRA system organ class (SOC).

It should be recognized that most studies are not designed to reliably demonstrate a causal relationship between the use of a pharmaceutical product and an adverse event or a group of

adverse events. Except for select events in unique situations, studies do not employ formal adjudication procedures for the purpose of event classification. As such, safety analysis is generally considered as an exploratory analysis and its purpose is to generate hypotheses for further investigation. The 3-tier approach facilitates this exploratory analysis.

6.10.2. Laboratory Data

Laboratory data will be listed and summarized in accordance with the CaPS. Summaries of subjects meeting pre-specified monitoring and discontinuation criteria will be created using methods for categorical data (see [Section 5.2.4](#)).

6.10.3. Vital Signs, including Height and Weight

Vital signs will be summarized at baseline, Weeks 2, 4, 8 and 12 / End of Treatment visits. Height and weight will be summarized at enrollment / baseline.

6.10.4. Electrocardiogram

ECG parameters, if applicable, will be summarized at baseline and End of Treatment visits.

6.10.5. Physical Examination

Physical examinations will be summarized at screening visits.

7. INTERIM ANALYSES

There will be no interim analyses for this study.

This study uses an External Data Monitoring Committee (E-DMC). The E-DMC will be responsible for ongoing monitoring of the efficacy, safety and PKs of subjects in the study according to the charter. Pharmacokinetic data from the first 20 adolescent subjects will be analyzed and reviewed by the E-DMC. The recommendations made by the E-DMC to alter the conduct of the study will be forwarded to Pfizer for final decision. Pfizer will forward such decisions, which may include summaries of aggregate analyses of endpoint events and of safety data that are not endpoints, to regulatory authorities, as appropriate. Composition of the E-DMC and processes under which the E-DMC operates will be documented in the E-DMC charter.

9. APPENDICES

Appendix 1. Summary of Clinical Efficacy Analyses

Efficacy Endpoints	Population	Analysis Method	Missing Data Imputation	Primary Analysis for Co-primary Endpoints
Week 12 IGA Response	FAS	CMH	NR	Yes
	PPAS	CMH	NR	No
	FAS	CMH	TP(MAR)	No
	FAS	CMH	TP(MNAR)	No
Week 12 EASI-75 Response	FAS	CMH	NR	Yes
	PPAS	CMH	NR	No
	FAS	CMH	TP(MAR)	No
	FAS	CMH	TP(MNAR)	No
Weeks 2, 4, 8 and 12 NRS4 for severity Response	FAS	CMH	NR+MI	
	PPAS	CMH	NR+MI	
	FAS	CMH	NR	
Week 12 CFBL in PSAAD	FAS	MMRM	OD	
	PPAS	MMRM	OD	
Time to NRS4 for severity	FAS	Kaplan-Meier	OD	
Weeks 2, 4 and 8 IGA Response	FAS	CMH	NR	
Weeks 2, 4, 8 and 12 EASI-50/EASI-90/EASI-100 Response	FAS	CMH	NR	
Weeks 2, 4 and 8 EASI-75 Response	FAS	CMH	NR	
Weeks 2, 4, 8 and 12 %CFBL in Total EASI Score	FAS	MMRM	OD	
Days 1 – 15, Weeks 4, 8 and 12 CFBL in NRS for severity	FAS	MMRM	OD	
Weeks 2, 4, 8 and 12 CFBL in %BSA	FAS	MMRM	OD	
Weeks 2, 4, 8 and 12 %CFBL in SCORAD Total Score	FAS	MMRM	OD	
Weeks 2, 4, 8 and 12 SCORAD50/SCORAD75 Response	FAS	CMH	NR	
Weeks 2, 4, 8 and 12 CFBL in SCORAD subjective VAS assessments of itch and sleep loss	FAS	MMRM	OD	
CFBL=Change from baseline; CMH=Cochran-Mantel-Haenszel; GLMM=Generalized Linear Mixed Models; ANCOVA=Analysis of Covariance; MMRM=Mixed-effect Model Repeated Measures; NR=Non-Responder; TP=Tipping Point; MAR=Missing At Random; MNAR=Missing Not At Random.				

Appendix 2. Definition and Use of Visit Windows in Reporting

Visit windows will be used for efficacy variables, and for any safety data that display or summarize by study visit. For other endpoints (eg, ECG, vital signs), visit windows will be applied for summary statistics by study visits if required.

Visit Label	Target Day	Definition [Day window]
Screening		Days -28 to Day -1
Baseline	Day 1 (Day of first dose)	Last observation prior to and including day of first dose
Week 2	15	Days 2 to 22
Week 4	29	Days 23 to 43
Week 8	57	Days 44 to 71
Week 12	85	Days 72 to 99
Follow Up/End of Study		
Week 16	-	Days 100 to -

For the lab values, if the calculated study day for the labelled baseline visit is not study Day 1, but falls within 28 days before the start of the study dosing, then that data should be used for the baseline instead of leaving baseline missing.

For the other values, if the calculated study day for the labelled baseline visit is not study Day 1, but falls before the start of the study dosing, then that data should be used for the baseline instead of leaving baseline missing.

If two or more visits fall into the same window, keep the one closest to the Target Day. If two visits are equaled distant from the Target Day in absolute value, the later visit should be used.

Safety analysis may follow Pfizer standards.

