- s. Site staff is to administer the C-SSRS, SBQ-R and PHQ-8 to all subjects at screening and score immediately. Subjects who have recent or active suicidal ideation or behavior or clinically significant depression will be excluded from the study or discontinued from the study per [Section 4.2](#), [Section 7.5.1](#), [Section 7.5.2](#) and [Section 7.5.3](#). For subjects meeting exclusionary results on the C-SSRS, SBQ-R and PHQ-8, it is recommended the subject's primary care physician (PCP) should be informed, and the subject referred to a mental health professional, either by the PCP or the investigator according to their usual practice.
- t. For subjects at selected study sites, photographs of treated AD will be obtained. Photographs will be utilized for illustrative purposes and not evaluated as an endpoint (see [Section 7.7.5](#)).
- u. Pruritus Numerical Rating Scale (NRS) and Night Time Itch Scale will be assessed using an eDiary, daily during the screening period and from Day 1 to 15. After Day 15, the pruritus NRS and Night Time Itch Scale will be completed only on study visit days in the eDiary. At the Screening visit, site staff will dispense the ePRO device and review instructions for completion of the subject eDiary for the NRS and Night Time Itch Scale. At every visit, the study coordinator will review the eDiary for completeness and counsel the subject on how to complete the items in the daily eDiary, if needed.
- v. Pruritus and Symptoms Assessment for Atopic Dermatitis (PSAAD) will be conducted to assess the severity and frequency of pruritus, symptoms and sleep collected daily in a subject e-diary during the screening period and from Day 1 through the End of Study visit in selected countries (See [Section 7.8.8](#)). At the Screening visit, site staff will dispense the ePRO device and review instructions for completion of the subject eDiary for the PSAAD questionnaire. Subjects will be asked to record their assessment in their eDiary once a day before taking the investigational product. At every visit, the study coordinator will review the eDiary for completeness and counsel the subject on how to complete the items in the daily eDiary, if needed.
- w. DLQI will be completed by adult subjects only. Adolescents 12-17 years of age will complete the CDLQI instead.
- x. SF-36v2 and WPAI:AD will be completed by adult subjects only. Adolescents 12-17 years of age will not complete these assessments.

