6.2.3. Visit 4, Day 15/Week 2 (±1 day)

- Administer PROs including PtGA, DLQI (or CDLQI), POEM, HADS and EQ-5D-5L (or EQ-5D-Y);
- Adolescents 12-17 years of age will complete the CDLQI instead of the DLQI and the EQ-5D-Y instead of the EQ-5D-5L;
- Review pruritus NRS, Night Time Itch Scale, and PSAAD completion (in selected countries) and review eDiary procedures with subject as necessary. Instruct subject that pruritus NRS and Night Time Itch Scale will now be completed only at visits on site and in the eDiary and will no longer be completed on a daily basis at home;

- Urine pregnancy test (female subjects of childbearing potential, including adolescents aged 12 years and older, regardless of whether they have experienced menarche). A negative urine pregnancy test must be obtained prior to dosing with the investigational product;
- Administer investigational product at clinic;
- Perform a single 12-lead electrocardiogram (ECG);
- Conduct targeted physical examination;
- Obtain samples for laboratory testing: serum chemistry, hematology (including coagulation panel), and urinalysis;
- Conduct clinical evaluations including IGA, SCORAD, EASI and BSA (calculated in the EASI);
- Photography of AD lesions (at selected sites; [Section 7.7.5](#));
- Obtain vital signs including pulse rate, blood pressure, respiratory rate and oral or tympanic temperature (after at least 5 minutes of rest). Vital signs must be performed at least 1 hour following administration of investigational product;
- Assess need for contraception and adherence to applicable lifestyle requirements ([Section 4.4](#)). Establish willingness and ability to comply with lifestyle requirements going forward in the study;
- Review any changes in the subject's concomitant medications and treatments information;
- Review eDiary to assess completion;
- Perform drug accountability procedures;
- Assess and record any Adverse Events since the last visit.

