9.2.3. Analysis of the Primary Endpoints

The co-primary endpoints will be analyzed using the (Cochran-Mantel-Haenszel) test adjusted by randomization strata (baseline disease severity and age) and both must achieve statistical significance to meet the primary objective. The difference between each active group and the placebo group in the proportion of subjects achieving IGA response (similarly for EASI75) along with its 95% confidence interval (using the normal approximation for the difference in binomial proportions) will be reported. If a subject withdraws from the study, then this subject will be counted as non-responder for endpoints after withdrawal. Additional secondary analyses will utilize Missing at Random and Not at Random approaches (eg, Longitudinal Mixed models and jump to reference analyses).

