5.3.1. Binary Endpoints

For binary endpoints analyzed at each scheduled visit separately, visit windows (see [Appendix 2](#)) will be used to map all observed data into nominal visits. After mapping, for subjects who drop out for any reason, any missing data will be defined as “non-responsive” from that point on at all subsequent visits; for other subjects, any observations missing intermittently (including baseline values) will be considered missing completely at random (MCAR) and will remain missing in the analysis.

Additional analyses that are based on statistical considerations will utilize the longitudinal nature of the binary endpoint. A Generalized Linear Mixed Model (GLMM) will be fit to the observed data (i.e., without defining missing data due to dropout as “non-response”). The binary outcome will be modeled using a logistic-normal distribution. Fixed factors will include treatment (PF-04965842 200 mg QD and 100 mg QD and the placebo group), visit (Weeks 2, 4, 8 and 12) and treatment-by-visit interaction. Visit will be modeled as a categorical covariate. A subject-specific random intercept will be used to model the correlation within a subject over time (see [Appendix 3](#)). Missing observations for the active groups will be imputed multiply using a tipping point analysis to estimate the treatment effect under the assumption that the missing data mechanism is missing at random (MAR) or more generally, is missing not at random (MNAR). Using the estimated posterior predictive distribution of the GLMM model parameters obtained using Markov Chain Monte Carlo (MCMC) methods, estimates of the posterior predictive probability of response will be calculated for each treatment group. For subjects with missing data at a visit, the posterior predictive response probability in each PF-04965842 dose group will be re-defined as a weighted linear combination of the posterior predictive response probability from this group and the posterior predictive response probability from the placebo group, where the missing observations in placebo group are assumed to be missing at random (MAR) (see [Appendix 3](#)). These weights are fixed MNAR quantities for the active groups. A single imputation of the missing value will be sampled from a Bernoulli distribution with this

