6.3. Key Secondary Efficacy Endpoints

6.3.1. Weeks 2, 4 and 12 NRS4 for severity Response

- Summary: Proportion of subjects with NRS4 for severity response at Week 2, 4 and 12.
- Population: Subjects from the FAS, PPAS with a baseline NRS score for severity ≥ 4 .
- Statistical Method: CMH and normal approximation in Section 5.2.1. Visit windows will be used as described in Appendix 2.
- Missing Data: Two analyses will be performed:
- Primary Analysis: Missing data arising due to subject dropout are considered “non-response”. For any other missing observations, a multiple imputation approach based on a GLMM will be used. (see the last two paragraphs within Section 5.3.1). This analysis will be based on both the FAS and the PPAS.

- Sensitivity Analysis: All missing data will be considered as “non-response”. This analysis will be based on the FAS only.

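### Read literally, the SAP's Week 2 window (Days 2 to 22) lets a daily itch score from an early dropout stand as Week 2 NRS4 data, against the protocol's non-responder rule; the passages need reconciling

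*SAP*

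**What the plan says.** **Recording.** The Schedule of Activities (Protocol, footnote u) has pruritus NRS entered in the eDiary "daily during the screening period and from Day 1 to 15", and after that on study visit days only. The Week 2 visit is Day 15 ±1 day (Protocol 6.2.3).

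**Windows.** SAP Appendix 2 states: "Visit windows will be used for efficacy variables". Week 2 has target Day 15 and window Days 2 to 22. The selection rule is: "If two or more visits fall into the same window, keep the one closest to the Target Day". There is no condition that the subject is still in the study. SAP 6.3.1 applies this to the key secondary NRS4 endpoint: "Visit windows will be used as described in" Appendix 2.

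**Order of steps.** SAP 5.3.1 says the windows "will be used to map all observed data into nominal visits". The dropout rule comes second: "After mapping, for subjects who drop out for any reason, any missing data will be defined as" non-response. For NRS endpoints, other gaps are multiply imputed under missing at random, or left missing when each group has 5 or fewer.

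**Protocol.** Section 9.2.3: "If a subject withdraws from the study, then this subject will be counted as non-responder for endpoints after withdrawal". Section 9.2.4 carries the same method to the 4-point pruritus response.

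**Role of the test.** SAP 5.1 tests Week 2 NRS4 for 200 mg against placebo at 2.5% once the co-primary endpoints succeed. The result decides whether Sequence A runs at 5% or 2.5%.

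**The concern.** The windows suit site visits two or four weeks apart. Applied to a daily diary, the Week 2 window takes in almost every post-baseline entry. Two kinds of subject are affected, both without a Day 15 record.

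- **Early dropouts.** Suppose a subject has baseline 8, scores 3 on Day 7 and withdraws on Day 8. Improvement is 8 − 3 = 5, so NRS4 is met. The Day 7 value lies in the window and nothing is closer to Day 15, so Week 2 is not missing after mapping and the non-response rule never acts. Protocol 9.2.3 would make this subject a Week 2 non-responder.
- **Subjects still in the study.** If the diary stops on Day 5 and the Day 15 record is lost, the Day 5 value stands as Week 2, in place of the handling that SAP 5.3.1 sets out for such gaps.

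The sensitivity analysis in SAP 6.3.1, which sets all missing data to non-response, does not reveal either case, because the value is not missing. What is at stake is the definition of a response in a gated key secondary test.

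**Working it through.** **1. The plan's own window boundaries.** Midpoints between target days:

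| Target days | Midpoint | Boundary in Appendix 2 |
|---|---|---|
| 1 and 15 | (1+15)/2 = 8 | Week 2 starts on Day 2 |
| 15 and 29 | (15+29)/2 = 22 | 22/23 |
| 29 and 57 | (29+57)/2 = 43 | 43/44 |
| 57 and 85 | (57+85)/2 = 71 | 71/72 |

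The last three boundaries follow the midpoint rule. The Week 2 start does not: the same rule gives Day 9. For the other daily diary, PSAAD, SAP Appendix 10 defines Week 2 as Days 9 to 15.

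**2. Which diary day becomes Week 2.** Take a dropout with daily entries through Day L, withdrawal dated on Day L, and no later value through Day 22. There are 13 possible days, L = 2 to 14. The last entry stands as Week 2 on:

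- current rule: 13 of 13 days;
- window starting on Day 9: 6 of 13 (Days 9 to 14);
- window starting on Day 9, with withdrawals before Day 14 set to non-response first: 1 of 13 (Day 14, inside the visit window).

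A subject with a Day 15 entry is unaffected under every version.

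**3. Effect of one credited dropout.** Planned sizes are 150 per active arm and 75 on placebo. Nearly all subjects should enter the NRS4 population, because entry requires a baseline score of at least 4.

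- Active: 1/150 = 0.67 points.
- Placebo: 1/75 = 1.33 points.
- One in each arm changes the difference by 0.67 − 1.33 = −0.67 points (unrounded inputs).
- Three on active and one on placebo change it by 2.00 − 1.33 = +0.67 points.

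**4. Range under assumptions.** The sample-size section covers only the co-primary endpoints, so there is no Week 2 NRS4 figure to reproduce. Assume 1% to 5% of an arm drops out before Day 15 and 10% to 50% of those meet NRS4 at the last entry. That arm's rate rises by between 0.01 × 0.10 = 0.1 points and 0.05 × 0.50 = 2.5 points.

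**5. Effect on the 2.5% test.** Pooled two-proportion z-test, two-sided, z = (p1 − p2)/√[p(1 − p)(1/150 + 1/75)], assumed counts:

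| 200 mg | Placebo | Reading | p |
|---|---|---|---|
| 28/150 | 6/75 | no one credited | 0.035 |
| 30/150 | 6/75 | two credited on 200 mg | 0.021 |
| 33/150 | 8/75 | five on 200 mg, two on placebo | 0.038 |
| 45/150 | 6/75 | clear effect, no one credited | 0.0002 |
| 47/150 | 6/75 | clear effect, two credited on 200 mg | 0.0001 |

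The first row was placed near the threshold on purpose. From there, two credited subjects on 200 mg alone cross 2.5%, while crediting in both arms slightly raises p. With a clear effect nothing changes.

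**The case against.** The strongest reply is that daily entries were never meant to fill Week 2. The Appendix 2 selection rule speaks of *visits*, and Days 2 to 14 of a diary are not visits. SAP 5.3.1 describes a device fault that lost NRS data at the scheduled Week 2 (Day 15) visit and later, and provides special handling for those gaps. If any earlier entry filled Week 2, few of those subjects would be missing there. SAP Appendix 1 also lists the Days 1 to 15 change-from-baseline analysis under its own labels. The Protocol section on the pruritus NRS is redacted, so it cannot settle the matter. This stands as evidence of intent. It does not remove the problem, because 5.3.1 says all observed data and no sentence limits mapping to visit-day entries. Even on a visits-only reading, an early termination visit before Day 23 falls in Week 2.

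Second, within the SAP the order is explicit: map first, then treat what is still missing. A windowed value therefore follows the SAP's own rule. That is correct. The conflict is with Protocol 9.2.3 and 9.2.4. Protocol Section 9 lets the SAP modify such analyses, but the SAP does not present this as a change.

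Third, a reader might infer that the rule favours active treatment, or inflates the Week 2 difference by some 0.4 to 1.5 points. The documents support neither. The rule is the same in all arms, and one placebo subject weighs twice as much as one active subject. Those figures come from assuming that 2% to 5% of each arm is affected, that the carried-forward response is 22 to 30 points higher on active, and that every affected subject is a dropout. For a subject still in the study, the comparison is with an imputed value or with no value, and the change may be near zero or negative.

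**Conclusion.** The point holds as a conflict of rules on a gated key secondary endpoint. Read literally, the SAP can credit a Week 2 NRS4 response to a subject who has already withdrawn, and can replace the planned handling of in-study gaps with an early value. Whether the authors intended this is unclear, so the passages must be reconciled; otherwise two programmers could build different Week 2 data sets from the same text.

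The size is unknown. It depends on early-loss and Week 2 NRS4 rates that the documents do not give. What follows from the design alone is 0.67 points per credited subject on an active dose and 1.33 on placebo, with the net direction open. A reader might go further and say that the 2.5% test, and with it Sequence A, is compromised. The documents do not support that: the outcome changes only if the result is already near the threshold. A miss would not end testing either, since Sequence A then runs at 2.5% and alpha can return to Week 2 NRS4 if the whole sequence succeeds.

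**What to change.** - **SAP Appendix 2:** give diary-based pruritus NRS its own Week 2 window, Days 9 to 22. Day 9 is the midpoint start and matches PSAAD. Keeping Day 22 as the end retains late Week 2 visits, which a Day 15 ±1 window would discard. State whether non-visit diary entries inside this window may represent Week 2.
- **SAP 5.3.1:** before windows are applied, set subjects who withdraw before the Week 2 visit window (before Day 14) to non-response at Week 2, and name the recorded date that counts as withdrawal. The Day 9 start alone is not enough, because it leaves Days 9 to 13 open to early dropouts.
- **Other gaps:** leave as 5.3.1 already states, with multiple imputation, or left missing when there are 5 or fewer per group.

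The cost is one table row and a few sentences, with no new data. A few more subjects become non-responders, imputed or missing at Week 2. Earlier daily values stay available for the time-to-NRS4 and daily change analyses.
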